2.2 Randomization

Patients are randomized with equal probability 1:1 to the two study arms. Randomization sequences were generated per study site and with block randomization applying varying block lengths of 2 to 4 assignments per study arm. The random sequences were generated in R with package “blockrand” version 3.5.2 and fed into the eCRF system which triggered the random assignments according to patient enrollment order.

2.3 Sample Size and Power Calculation

We plan to enroll an adequate number of patients for the study by a Bayesian adaptive design with a maximum number of 700 patients and interim analyses after the enrollment of 200 patients, 350 patients, 550 patients and 650 patients.

Sample size estimation was done in two steps:

- (a) An initial rough estimate of study size, based on results from the pilot study for the three main endpoints (primary endpoint, and first and second secondary endpoints) and conducted for a Bayesian design with fixed sample size (samples with 200, 300, 400, 500, 600, and 700 patients).

Results were summarized in the study protocol Section 8.8 and are repeated in this SAP in Section 2.3.1.

(b) A final comprehensive examination of study characteristics of the adaptive Bayesian study design related to type-I error, statistical power and study size. In the context of these investigations, the decision parameters for final study success (" γ ") and for stopping early for futility or out of success (" Θ^r " and " Θ^s ") were set in such a way that the type-I error was controlled at the 2.5% level and, in addition, sufficient statistical power resulted with acceptable study size, see Section 2.3.2.

2.3.1 Initial Estimation

Sample size estimation was based on the observed results of the first two ProSAVE pilot-level study batches, see Table 2.1 (analysis population and endpoint specific results; "ProSAVE-1 & -2" comprising 95 (ITT) and 60 (PP) non-COVID patients not transferred to ICU within 24 hours, patients enrolled from 2020-05-28 to 2021-02-24). 5000 clinical trials were simulated per analysis setting (study endpoint, analysis population and assumed fixed sample size from 200 to 700 patients) with the distribution of events according to predictive posterior distributions (computed for the assumed sample sizes from pilot posterior probability distributions derived with uninformative conjugate priors). The corresponding statistical power estimates were determined as the proportions of study successes when applying Bayesian superiority testing to the three endpoints CAE30, shortABx and prescribedABx (one-sided at 2.5% significance level, i.e., with $\gamma = 0.975$).

We consider a sample size of about 500 patients to be adequate for the study because a statistical power of 90% was reached with 500 patients for the safety endpoint CAE30 assuming pilot ITT results, see Table 2.2.

In order to account for additional sources of variation and missing data, e.g. due to seasonal changes during the year, possible influences of a potential fourth wave of COVID-19 and the inclusion of additional study sites, we specify the study design in an adaptive way with planned interim analyses after 200, 350, 550 and 650 patients and a maximum number of 700 enrolled patients.

Table 2.1: Pilot study results for the safety endpoint "CAE30" and for the antibiotic exposure endpoints "shortABx" and "prescribedABx" for ITT and PP patient populations.

Simulation scenario			Pilot study results			
n	Endpoint	Data	PCT		Control	
			n	n _{pos}	n	n _{pos}
1	CAE30	pilot, ITT	48	3	47	10
2		pilot, PP	30	1	30	7
3	shortABx	pilot, ITT	48	14	47	5
4		pilot, PP	30	12	30	3
5	prescribedABx	pilot, ITT	47	15	46	24
6		pilot, PP	30	7	29	19

Table 2.2: Estimation of statistical power in terms of assurance probability (i.e. proportion of simulated trials reaching study success) for the three study endpoints "CAE30", "shortABx" and "prescribedABx" with fixed sample sizes from 200 to 700

patients (total; 100 to 350 patients per study arm) assuming effect sizes (estimate and uncertainty) of the “ProSAVE-1 & -2” pilot data results.

Data	# Patients		Statistical Power		
	Total	Per arm	CAE30	shortABx	prescribedABx
pilot, ITT	200	100	79%	82%	76%
	300	150	84%	86%	81%
	400	200	87%	90%	86%
	500	250	90%	92%	87%
	600	300	91%	93%	88%
	700	350	92%	94%	90%
pilot, PP	200	100	88%	94%	98%
	300	150	91%	96%	99%
	400	200	93%	97%	99%
	500	250	93%	98%	100%
	600	300	95%	98%	99%
	700	350	95%	98%	100%

2.3.2 More Precise Estimation for the Adaptive Design with CAE30 Superiority Testing

The cut-off parameters of final and interim analyses, γ , Θ^F and Θ^S , were specified by numerical simulations to assure a sufficiently controlled one-sided type-I error < 2.5% and a sufficiently high statistical power (study success probability). The simulations were conducted assuming different study-arm specific binary probabilities, of CAE30 events, occurrence of short antibiotic treatment and occurrence of discharge-prescribed antibiotic treatment, as strong as observed in the pilot study or of smaller effect size, e.g. half the effect size observed in the pilot study, see below.

The main simulation settings for power and type-I error evaluation were as follows:

1. Patient enrollment times were generated using a piece-wise uniform distribution with a rate of 25 patients per month for the first 7 months, 35 patients for month 8, 45 patients for month 9 and 65 patients per month thereafter.
2. Times to CAE30 for patients of the Control arm were generated using an exponential distribution with rate of 0.01 per month. These were censored by LoS data which were generated using an exponential distribution with rate = 0.12 (from pilot trial). For the PCT arm different relative risks (RR) relative to the Control arm were used to generate the CAE30 data.
3. Short and prescribed ABx data for the PCT arm and the Control arm were generated according to the observed rates in the pilot trial, and in an additional scenario with smaller differences between study arms than observed in the pilot trial.
4. Simulation for each scenario under the null (RR=1) and alternatives (RR=0.27, 0.4, 0.5, 0.6) were replicated 10,000 times and average type-I error rate and power were reported.

In addition, simulations were conducted for a lower CAE30 event rate of 12% (minimal possible event rate estimated by the study PI) instead of 20% (observed in the pilot study) for the Control arm to explore corresponding changes in study power.

Under the null (RR=1) various γ values were examined, see Table 2.3. $\gamma = 0.9785$ was chosen with an estimated type-I error of $2.48\% < 2.5\%$.

Table 2.3: Fine tuning of the parameter γ specifying study success: estimated type-I errors.

γ	Type-I Error
0.9781	0.0256
0.9782	0.0256
0.9783	0.0253
0.9784	0.0251
0.9785	0.0248
0.9786	0.0248
0.9787	0.0247
0.9788	0.0245
0.9789	0.0245

Assuming the observed effects of the pilot trial (scenario RR = 0.27 in Table 2.4) the overall power of the trial with 700 enrolled patients is about 100% and the probability to stop the trial with 500 patients with success for the primary endpoints CAE30 and the first two secondary endpoints shortABx and prescribedABx is 92%.

If the true relative risk for CAE30 were 0.4, 0.5 or 0.6 instead, then the design would still achieve 99%, 93% and 76% overall statistical power, respectively, and the probabilities to stop with 500 enrolled patients would be 82%, 63% and 40%, respectively.

If the true effects of all three endpoints CAE30, shortABx and prescribedABx were weaker than observed in the pilot study (more specifically: $p_{Ctrl} = 0.20$ vs. $p_{PCT} = 0.10$ for CAE30 (ratio = 0.5), $p_{Ctrl} = 0.11$ vs. $p_{PCT} = 0.20$ for shortABx (ratio = 1.8) and $p_{Ctrl} = 0.51$ vs. $p_{PCT} = 0.41$ for prescribedABx (ratio = 0.8)), then the design would provide 93% statistical power for CAE30, 84% statistical power for shortABx and 62% statistical power for prescribedABx (corresponding to the hierarchical testing of study endpoints). The probability of stopping early with success with 500 enrolled patients would be about 19%.

Table 2.4: Adaptive design power for $\gamma = 0.9785$, $\Theta^F = 0.1$ and $\Theta^S = 0.9$ and non-binding futility with different alternative assumptions: according to “RR” for CAE30 and according to pilot study results for shortABx and prescribedABx.

Abbreviations: RR = relative risk for simulation of CAE30 events; type = analysis stage with 700 patients (“overall”) and at the different interim analysis (IA) stages with 200, 350, 500 and 600 patients; power.cae = statistical power for CAE30 under the alternative with specified RR, overall and at each interim; power.sabx = statistical power for shortABx under the alternative with pilot study results, overall and at each interim; power.pabx = statistical power for prescribedABx under the alternative with pilot study results, overall and at each interim; fut.trig.prob = probability of meeting futility criteria

Adaptive Design Power with $\Theta_N^F = 0.1$ and $\Theta_N^E = 0.9$

Non-binding Futility

RR	type	power.cae	power.sabx	power.pabx	fut.trig.prob
0.27	overall	1	1	0.9976	0.0023
	IA.200				0.0022
	IA.350				0.0001
	IA.500	0.9218	0.9218	0.9215	0.0000
	IA.600	0.0542	0.0542	0.0542	0.0000
0.4	overall	0.9919	0.9917	0.9876	0.0188
	IA.200				0.0125
	IA.350				0.0034
	IA.500	0.819	0.819	0.8187	0.0016
	IA.600	0.1129	0.1128	0.1126	0.0013
0.5	overall	0.9348	0.9346	0.9297	0.0727
	IA.200				0.0346
	IA.350				0.0153
	IA.500	0.6324	0.6324	0.6319	0.0143
	IA.600	0.1535	0.1535	0.1534	0.0085
0.6	overall	0.756	0.7556	0.7502	0.2038
	IA.200				0.0762
	IA.350				0.0445
	IA.500	0.3967	0.3967	0.3963	0.0434
	IA.600	0.1552	0.1552	0.1551	0.0397

Simulation results provided by Cytel

Table 2.5: Adaptive design power for $\gamma = 0.9785$, $\Theta^F = 0.1$ and $\Theta^S = 0.9$ and non-binding futility with the additional alternative assuming that the effects of the three endpoints CAE30, shortABx and prescribedABx are weaker than observed in the pilot study; more specifically the assumptions were (a) for CAE30: $p_{Ctrl} = 0.20$ vs. $p_{PCT} = 0.10$, (b) for shortABx: $p_{Ctrl} = 0.11$ vs. $p_{PCT} = 0.20$, (c) for prescribedABx: $p_{Ctrl} = 0.51$ vs. $p_{PCT} = 0.41$.

Abbreviations: as in Table 2.4

Add. Scenario, Adaptive Power, $\Theta_N^F = 0.1$, $\Theta_N^E = 0.9$

Non-binding Futility

RR	type	power.cae	power.sabx	power.pabx	fut.trig.prob
0.5	overall	0.9304	0.8422	0.6214	0.0710
	IA.200				0.0350
	IA.350				0.0160
	IA.500	0.1892	0.1886	0.186	0.0118
	IA.600	0.1578	0.1572	0.154	0.0082

Simulation results provided by Cytel

2.3.3 Update for Protocol Changes (2022-12-20)

Additional clinical trial simulations were conducted to assess if the specified study design would still be adequate and provide reasonable statistical power when then following study protocol changes were conducted: (a) exchange of primary endpoint and first secondary endpoint (new primary endpoint: shortABx, new first secondary endpoint: CAE30), (b) change of CAE30 inference from superiority to non-inferiority, and (c) change of the times of interim analyses from 500 and 600 patients to 550 and 650 patients, respectively. The simulations were conducted analogously to the ones described in the previous subsection (clinical trial Monte Carlo simulations based on pilot study results) including some improved approximations of data generation according to current study knowledge (blinded analysis results of IA350 data in addition to pilot results: enrollment rate held constant at one patient per day, marginal endpoint rates over both study arms set to 20% for CAE30, 22% for shortABx and 40% for prescribedABx) and of protocol implementation (inclusion of five follow-up days of last enrolled patient at interim analysis according to data transfer experience).

Bayesian CAE30 superiority testing

Probability(CAE30 probability of PCT arm < CAE30 probability of Control arm) > γ

was replaced by CAE30 non-inferiority testing with $M = 10\%$ non-inferiority margin

Probability(CAE30 probability of PCT arm < CAE30 probability of Control arm + M) > γ ,
 $M = 0.1$.

The protocol changes required a re-specification of the analysis parameter γ to assure type-I error rate control at 2.5% (new order of hierarchical testing of endpoints: first shortABx, then CAE30, then prescribedABx; null hypothesis for shortABx instead of CAE30; interim and final CAE30 NI analyses on PP populations; interim analyses with 550 and 650 patients). Under the null for the primary study endpoint shortABx (relative risk of shortABx for PCT arm versus Control arm set to 1) and under the additional conservative assumptions of effects of CAE30 and prescribedABx as in the pilot study ($RR_{CAE30} = 0.30$, $RR_{prescribedABx} = 0.60$; PCT arm versus Control arm) and the PP population as a random subset of 50% of the patients of the full population (50% estimated for the running study), a γ value of 0.985 was determined to keep the type-I error rate below 2.5% (increase of γ vs. previous protocol version from 0.9785 to 0.985; γ estimated by linear regression of type-I error rate vs. specified γ values based on Monte Carlo runs with 50,000 simulated clinical trials).

Moreover, simulations showed that adequate statistical power could be achieved even for small CAE30 effects. Assuming (a) half of the shortABx effect observed in the pilot study ($RR_{shortABx} = 1.9$), (b) only one tenth of the CAE30 effect observed in the pilot study ($RR_{CAE} = 0.9$), (c) half the prescribedABx effect observed in the pilot study ($RR_{prescribedABx} = 0.80$), and (d) the PP population as a random subset of 50% of the patients of the full population (50% PP patients estimated for the running study), we obtained 99% statistical power for shortABx superiority on ITT population, 75%

for CAE30 non-inferiority on PP population, and 48% for prescribedABx superiority on ITT population. The following Table 2.6 gives an overview of the study design characteristics of this scenario.

Table 2.6: Characteristics of the study design with protocol changes (sABx as primary endpoint, CAE30 non-inferiority testing with 10% NI margin, IA with 550 and 650 patients, and $\gamma = 0.985$) assuming (a) half the effect observed in the pilot study for shortABx ($RR_{shortABx} = 1.9$), (b) only one tenth of the CAE30 effect observed in the pilot study ($RR_{CAE} = 0.9$), (c) half the effect observed in the pilot study for prescribedABx ($RR_{prescribedABx} = 0.80$), and (d) the PP population as a random subset of 50% of the patients of the full population. Interim, final and total results in rows, first two columns to describe the level of analysis, columns three to five for the probabilities of meeting endpoint-specific study success criteria (hierarchical testing: (1) shortABx superiority on ITT population, (2) CAE30 non-inferiority on PP population, (3) prescribedABx superiority on ITT population, columns six to eight for outcomes of interim analyses.

Abbreviations: “IA” for “interim analysis”, “IA-200” for “IA with 200 enrolled patients”, “End-700” for “final analysis with 700 enrolled patients”, “-” for “not applicable” and “recom.” for “recommendation”.

Level of Analysis		Results						
Stage of Analysis	# PP Patients	Probability of Meeting EP Success Criteria			Interim Analysis Outcome			Efficacy
		sABx	CAE30	pABx	Futility recom.	Study stopped		
IA-200	100	-	-	-	7%	-	0%	
IA-350	176	-	-	-	8%	-	0%	
IA-550	276	27%	27%	27%	12%	27%	27%	
IA-650	324	12%	12%	12%	15%	12%	12%	
End-700	350	59%	36%	9%	-	-	-	
Total	-	99%	75%	48%	-	39%	39%	

2.4 Framework of Statistical Inference

The main analyses of the study comprise statistical testing of the treatment “PCT arm” versus the “Control arm” concerning the following three binary endpoints: (a) the primary endpoint short antibiotic treatments (shortABx), (b) the first secondary endpoint composite adverse events “CAE30”, and (c) the second secondary endpoint of antibiotic prescription at discharge (prescribedABx). See Section 4.1 for the definition of the endpoints.

The endpoints will be tested in a hierarchical manner: first, superiority testing will be conducted for the primary endpoint shortABx (see Section 4.4 "Primary Analysis"). If superiority is concluded for shortABx, then non-inferiority testing will be conducted for the first secondary endpoint CAE30 (see Section 4.5). If non-inferiority is concluded for CAE30, then superiority testing will be conducted for the second secondary endpoint prescribedABx (see Section 4.6). This hierarchical testing scheme allows to test the three endpoints without correction for multiple testing.

A more detailed description of the analyses is given below.

2.5 Statistical Interim Analyses and Early Stopping Guidance

Interim analyses are planned with about 200 patients, 350 patients, 550 patients and 650 patients. Follow-up data will be considered according to their availability at the times when the interim analyses will be performed. A maximum number of 700 patients will be enrolled in the study. The interim analyses will be conducted to check for early stopping due to futility and/or success.

After the enrollment of 200 and 350 patients an interim analysis will be conducted applying a criterion for potentially *stopping for futility*. A recommendation to stop enrollment of patients for the study will be given to the principal investigator if interim results are in the futility zone to reach the CAE30 success criterion. Here, success refers to showing non-inferiority with non-inferiority margin $M = 10\%$. More specifically, a recommendation to stop patient enrollment will be given if the posterior predictive probability of CAE30 success with the maximum number of 700 patients is below the futility cut-off $\Theta^F = 0.1$:

Probability(CAE30 success with 700 patients | interim data) $< \Theta^F$, i.e.

Probability(Posterior predictive probability($p_{pct} < p_{crit} + M$, 700 patients | interim data) $> \gamma$) $< \Theta^F$,
with $\gamma = 0.985$ and $M = 0.1$ (10% non-inferiority margin).

Note that the simulations of study design characteristics, and in particular the specification of γ for type-1 error control at a one-sided level of 2.5%, were conducted with non-binding stopping for futility (i.e., simulated clinical trials were never stopped for meeting the futility criterion). Accordingly, when given study recommendations to stop patient enrollment for futility will be non-binding.

After the enrollment of 550 and 650 patients an interim analysis will be conducted applying criteria to stop potentially (a) for futility or (b) for study success:

a. ***Stopping for futility***

A recommendation to stop patient enrollment for futility will be given if interim results are in the futility zone to reach the CAE30 success criterion. More specifically, a recommendation to stop patient enrollment will be given if the posterior predictive probability of CAE30 success to show non-inferiority with the maximum number of 700 enrolled patients is below a specific futility cut-off $\Theta^F = 0.1$:

Probability(CAE30 success with 700 patients | interim data) < Θ^F , i.e.

Probability(Posterior predictive probability($p_{PCT} < p_{ctrl} + M$, 700 patients | interim data) > γ) < Θ^F , with $\gamma = 0.985$ and $M = 0.1$ (10% non-inferiority margin).

b. Stopping for success

Enrollment will be stopped for success if interim results reveal a sufficiently high predictive probability that success criteria can be reached for the endpoints CAE30, shortABx and prescribedABx with the currently enrolled patients. More specifically, enrollment will be stopped if the posterior predictive probabilities of the three endpoints CAE30, shortABx and prescribedABx for the respective number of enrolled patients are above the specific success cut-off $\Theta^S = 0.9$:

Probability(CAE30 success with enrolled patients | interim data) > Θ^S AND

Probability(shortABx success with enrolled patients | interim data) > Θ^S AND

Probability(prescribedABx success with enrolled patients | interim data) > Θ^S .

Note: A final analysis will still be conducted following an early stopping decision at any interim after all enrolled patients have completed their respective follow-up of 30 days.

Note: Use of the posterior predictive probability will allow to conduct the interim analysis in a timely manner without the need to wait for the completion of the 30 days follow-up times of all patients. Thereby, missing or incomplete endpoint data of enrolled patients will be imputed by predicted endpoint data including its respective level of uncertainty.

Posterior predictive probabilities for the safety endpoint CAE30 will be calculated as follows:

1. Computation of predictive distributions:

a. For patients still to be enrolled for a maximum of 350 + 350 study patients the following equation will be used to determine the beta-binomial predictive distribution (see e.g. [Cowles2013] p. 62, or [Rajat2021] section 3.1):

$$BBP(x'_i | n'_i, x_i, n_i) = \binom{n'_i}{x'_i} \frac{Beta(x'_i + x_i + 1, n'_i - x'_i + n_i - x_i + 1)}{Beta(x_i + 1, n_i - x_i + 1)} \quad (1)$$

with

i : index for study arm (“PCT arm” or “Control arm”),

n'_i : number of patients still to be enrolled for study arm i ,

i.e. 350 – number of patients enrolled for study arm i until interim analysis,

x'_i : number of patients with events among the n'_i patients still to be enrolled for study arm i ,

n_i : number of patients of study arm i with complete follow-up data,

x_i : number of patients of study arm i with complete follow-up data and observed events,

$Beta(,)$: beta function.

b. For already enrolled patients with partial follow-up data and no observed CAE30 yet, the following equation (2) will be applied with variables ... depending on follow-up time to determine the beta-binomial predictive distribution (analogous to (a) but with interim data adequately conditioned on follow-up time, see e.g. [Rajat2021] section 3.2):

$$BBP(x'_{i(t_j)} | n'_{i(t_j)}, x_{i(t_j)}, n_{i(t_j)}) = \binom{n'_{i(t_j)}}{x'_{i(t_j)}} \frac{Beta(x'_{i(t_j)} + x_{i(t_j)} + 1, n'_{i(t_j)} - x'_{i(t_j)} + n_{i(t_j)} - x_{i(t_j)} + 1)}{Beta(x_{i(t_j)} + 1, n_{i(t_j)} - x_{i(t_j)} + 1)} \quad (2)$$

with

i : index for study arm ("PCT arm" or "Control arm"),

$t = (t_1, t_2, \dots, t_p)$: vector of p distinct partial follow-up times (in days, $t_p < 30$),

$n'_{i(t_j)}$: number of enrolled patients of study arm i with partial follow-up data and without event until time t_j ,

$x'_{i(t_j)}$: number of patients with events after time t_j among the $n'_{i(t_j)}$ patients of study arm i with partial follow-up data and without event until time t_j ,

$n_{i(t_j)}$: number of patients with complete follow-up data and without event until time t_j ,

$x_{i(t_j)}$: number of patients with events after time t_j among the $n_{i(t_j)}$ patients with complete follow-up data without event until time t_j ,

$Beta(,)$: beta function.

The main idea behind this computation is to apply the equation (1) presented in a. in order to compute time-dependent posterior probabilities and posterior predictive probabilities that depend on the follow-up times of adequately censored patients (the more follow-up time has already passed, the less likely it is to still observe an event).

2. With the predictive distributions we will conduct Monte Carlo simulations, e.g. simulate the number of adverse events per study arm for many (e.g. 1e6) trials with maximum number of 350 + 350 patients. The number of events per study arm is the sum of three components: (i) the number of already observed events, (ii) the number of events predicted for patients yet to be enrolled and (iii) the number of events predicted for patients with partial follow-up data. The number of events according to (i) is fixed for all trials while the number of events according to (ii) and (iii) varies between trials and is sampled according to the posterior predictive distributions.
3. The posterior predictive probability of study success is estimated by the proportion of simulated trials with 350 patients enrolled per study arm meeting study success criteria with $\gamma = 0.985$.

Analogous computations will be conducted for the other two main study endpoints shortABx and prescribedABx.

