8.9 Interim Analyses

Interim analyses will be conducted after the enrollment of 200 patients, 350 patients, 550 patients and 650 patients.

After the enrollment of 200 and 350 patients an interim analysis will be conducted applying a criterion for potentially *stopping for futility*. A non-binding recommendation to stop patient enrollment for futility will be given if interim results are not in a “promising zone” to reach the CAE30 success criterion. More specifically, the stopping recommendation will be given if the posterior predictive probability of CAE30 success (i.e., proving non-inferiority) with the maximum number of 700 patients is below a specific futility cut-off $\Theta_{F_N} = 0.1$ with $N = 200$ or 350 representing the respective enrollment status:

Probability(CAE30 success with 700 patients | interim data) $< \Theta_{F_N}$, i.e.

Probability(Posterior predictive probability($p_{PCT} < p_{ctrl} + 0.1$, 700 patients | interim data) $> 98.5\%^1$) < 0.1

After the enrollment of 550 and 650 patients an interim analysis will be conducted applying criteria to stop potentially (a) for futility or (b) for study success:

a. *Stopping for futility:*

A non-binding recommendation to stop patient enrollment for futility will be given if interim results are not in a “promising zone” to reach the CAE30 success criterion. More specifically, enrollment will be stopped if the posterior predictive probability of CAE30 success with the maximum number of 700 enrolled patients is below a specific futility cut-off $\Theta_{F_N} = 0.1$ with $N = 550$ or 650 representing the respective enrollment status:

Probability(CAE30 success with 700 patients | interim data) $< \Theta_{F_N}$, i.e.

Probability(Posterior predictive probability($p_{PCT} < p_{ctrl} + 0.1$, 700 patients | interim data) $> 98.5\%^1$) < 0.1

b. *Stopping for success:*

Enrollment will be stopped for success if interim results reveal a sufficiently high probability that success criteria are reached for the endpoints CAE30, shortABx and prescribedABx. More specifically, enrollment will be stopped if the posterior predictive probabilities of the three endpoints CAE30, shortABx and prescribedABx for the respective number

of enrolled patients are above the cut-off $\Theta^s_N = 0.9$:

Probability(CAE30 success with enrolled patients | interim data) > Θ^s_N AND
Probability(shortABx success with enrolled patients | interim data) > Θ^s_N AND

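### The futility rule at 550 and 650 patients triggers on CAE30 alone, although shortABx is now the primary endpoint and first gate; Protocol 8.9(a) also words the rule as both non-binding and mandatory

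*SAP*

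**What the plan says.** SAP 2.4 sets the testing order: shortABx superiority first, and "If superiority is concluded for shortABx, then non-inferiority testing will be conducted for the first secondary endpoint CAE30". prescribedABx comes third.

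SAP 2.5 defines futility at all four looks by CAE30 only: a recommendation to stop enrollment "will be given if interim results are in the futility zone to reach the CAE30 success criterion". At 550 and 650 patients the trigger is that the predictive "probability of CAE30 success to show non-inferiority with the maximum number of 700 enrolled patients is below a specific futility cut-off" of 0.1. The target is the current one: "Here, success refers to showing non-inferiority with non-inferiority margin" of 10%. Protocol 8.9 gives the same criterion.

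shortABx enters only the stopping rule for success, where the predictive probabilities of all three endpoints must exceed 0.9. SAP 2.5 does, however, end by prescribing for shortABx and prescribedABx computations analogous to those for CAE30.

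On status, SAP 2.5 and 2.6 call futility non-binding. Protocol 8.9(a), on the 550 and 650 looks, first describes a non-binding recommendation. Its next sentence says "enrollment will be stopped if the posterior predictive probability of CAE30 success with the maximum number of 700 enrolled patients is below" the cut-off. The Protocol's paragraph on the 200 and 350 looks has no such conflict.

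**The concern.** When CAE30 was the primary endpoint, futility on CAE30 was futility on the primary. After the exchange it is futility on the second link of the chain. If shortABx fails, neither CAE30 nor prescribedABx can be formally tested, whatever CAE30 shows. A rule that does not use shortABx data can flag such a trial only by coincidence, through CAE30.

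At stake are further patients enrolled into a trial whose hierarchical claims are out of reach: up to 150 after the 550 look and up to 50 after the 650 look. The wording conflict matters because it concerns the instruction to be followed when the rule fires, which SAP Table 2.6 puts at 12% (550) and 15% (650) in the planning scenario.

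The point is confined to 550 and 650. The SAP version history reports the 350-patient look as already done under the previous objective.

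**Working it through.** **Inputs.** From SAP 2.3.3: "marginal endpoint rates over both study arms set to 20% for CAE30, 22% for shortABx and 40% for prescribedABx"; relative risks of 1.9 for shortABx ("half of the shortABx effect observed in the pilot study"), 0.9 for CAE30 and 0.80 for prescribedABx; a per-protocol (PP) population that is a random 50% of patients; and a "value of 0.985 was determined to keep the type-I error rate below 2.5"%. From SAP 2.5: futility cut-off 0.1, margin 10 points, maximum 350 per arm. shortABx is analysed on ITT and CAE30 on PP. Assumptions of this check: independent endpoints and, in the simulation, about 13 patients per arm with incomplete CAE30 data and 4 with incomplete antibiotic data at each look.

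**Arm rates.** With marginal rate m and relative risk RR, control = 2m/(1 + RR) and PCT = RR × control.
- shortABx: 0.44/2.9 = 15.2% control, 28.8% PCT.
- CAE30: 0.40/1.9 = 21.1% control, 18.9% PCT.

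**Reproducing Table 2.6.** The threshold 0.985 corresponds to z = 2.170.
- shortABx, 350 per arm: (0.1366 − 2.170 × √(2 × 0.22 × 0.78/350)) / √((0.1517 × 0.8483 + 0.2883 × 0.7117)/350) = 2.22, power 98.7% (stated 99%).
- CAE30, 175 PP patients per arm: (0.10 + 0.0211)/√((0.2105 × 0.7895 + 0.1895 × 0.8105)/175) − 2.170 = 0.66, power 74.6% (stated 75%).
- A simulation of the adaptive design (6,000 trials, uniform priors, beta-binomial prediction) gave futility recommendations in 7.2%, 7.6%, 11.2% and 15.6% of trials at the four looks (stated 7%, 8%, 12%, 15%). It gave 44.8% power for prescribedABx (stated 48%) and a 20.9% success stop at 550 (stated 27%). These two are not matched, and no error is claimed, because the SAP does not give its endpoint correlation or full data-lag settings. Neither figure enters the argument.

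**Simulated futility flags at 550 / 650.**

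| Scenario (RR) | Current CAE30 rule | Separate shortABx criterion, cut-off 0.1 |
|---|---|---|
| shortABx 1.9, CAE30 0.9 (planning) | 11.2% / 15.6% | 0.4% / 0.6% |
| shortABx 1.0, CAE30 0.9 | 10.7% / 14.6% | 91.0% / 95.7% |
| shortABx 1.0, CAE30 1.0 | 21.8% / 28.4% | 90.6% / 96.0% |
| shortABx 1.0, CAE30 0.3 (SAP type-I error scenario) | 0% / 0% | 89.9% / 95.5% |

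The first two rows show that the current rule fires about equally often whether or not shortABx works. A further simulation of the second row gave 12% and 14% for the current rule and 90% and 96% for the shortABx criterion.

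**Check by hand.** With flat priors and information fraction t, predictive probability below 0.1 means an interim z below 2.170√t − 1.2816√(1 − t).
- 550: t = 275/350 = 0.786, critical z = 1.330. 650: t = 325/350 = 0.929, critical z = 1.749.
- No shortABx effect: Φ(1.330) = 90.8% and Φ(1.749) = 96.0%.
- shortABx RR 1.9: expected z = 0.1366/√(0.3339/275) = 3.92 and 0.1366/√(0.3339/325) = 4.26, so Φ(1.330 − 3.92) = 0.5% and Φ(1.749 − 4.26) = 0.6%.

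**What a shortABx flag means.** Of the no-effect trials that the shortABx criterion flagged at 550, about 0.1% or fewer met the shortABx criterion at the end. With CAE30 RR 0.9, 81% of trials at 550 and 82% at 650 were futile on shortABx but not flagged by the current rule.

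**The case against.** Several arguments on the other side have force.

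- *The rule was reworked.* A reader might infer that it is an untouched leftover. It is not: the version that exchanged the endpoints also moved the target to non-inferiority, shifted the later looks to 550 and 650 and clarified the non-binding status, and Table 2.6 reports how the rule behaves. What remains is that it was not adapted to the new gate. The documents give no reason for that.
- *shortABx is not invisible.* A reader might infer that nothing at the looks would reveal a failing primary. The analogous computations in SAP 2.5 would show a near-zero predictive probability. What is missing is a formal trigger.
- *CAE30 is the weaker link.* Planned power is 99% for shortABx against 75% for CAE30, so watching CAE30 is a defensible preference, and the large contrasts arise only outside the planning scenario. This stands, and it limits the weight of the point. But a futility rule is meant for the case where planning assumptions fail.
- *The stakes are bounded.* Futility is non-binding, so there is no effect on type-I error. Other secondary and economic analyses lie outside the hierarchy; only CAE30 and prescribedABx are gated. The figures of 150 and 50 patients are upper bounds, since enrollment continues during the data lag.
- *The Protocol conflict is editorial.* A reader might infer that the status of the rule is open. It is not: the preceding sentence in 8.9(a) and SAP 2.5 and 2.6 all say non-binding. The sentence is still wrong as it stands, in the text governing a decision rule.

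**Conclusion.** Two conclusions hold. First, the futility rule at 550 and 650 does not use the primary endpoint. With no shortABx effect and CAE30 RR 0.9 it flags about 11–12% and 14–15% of trials, and none with CAE30 RR 0.3, against about 90% and 96% for a separate shortABx criterion that costs about 0.5% in the planning scenario. These figures rest on independent endpoints, the SAP's marginal rates and a 50% PP fraction. This is a cheap improvement to a defensible design, not an error that threatens the inference. Second, the mandatory wording in Protocol 8.9(a) is wrong as written, because it contradicts the sentence before it and the SAP.

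The documents do not support reading this as inflated type-I error, as a rule nobody revised, or as a certain loss of 150 patients.

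**What to change.** In SAP 2.5 and Protocol 8.9, for the 550 and 650 looks, add that a non-binding recommendation to stop is also given if the predictive probability of shortABx superiority (ITT) at 700 patients is below 0.1. Keep the CAE30 criterion; either one triggers.

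Keep the criteria separate. A single joint probability of both successes would need a joint model for an ITT endpoint and a PP endpoint, which the SAP does not specify. It can also fire when neither endpoint is futile (0.3 × 0.3 = 0.09). In simulation at 550 with shortABx RR 1.4, that happened in about 4% of trials, and about 30% of those still won the primary.

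In the futility paragraph of Protocol 8.9(a), replace the mandatory clause with a statement that a non-binding recommendation to stop enrollment will be given.

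The cost is a few lines in each document and about 0.5 point more flags in the planning scenario. The shortABx prediction is already prescribed in SAP 2.5. The threshold of 0.985 and the type-I error stay as they are, because the SAP simulations never stop a trial for futility.
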